2.1.5.8 Phone Call Follow-Up

Participants who have no evidence of TTR CA and/or are not V122I mutation carriers will be followed-up by phone at 6 and 12 months to gather information about vital status and document reasons and dates of hospitalizations (if any occurred).

2.1.6 Hypotheses

Aim 1: To determine the prevalence of ATTR CA in Caribbean Hispanics and Blacks with HF

Hypothesis 1. Overall prevalence of ATTR CA: The prevalence of ATTR CA will be defined by the number of cases with both ATTRwt and ATTRm CA as a percentage of total enrollment. The background prevalence of Val122Ile in the US Black population is 3.4%, and we hypothesize a prevalence rate of 8% of ATTRm Val122Ile in our outpatient HF population. Since there are no data in Hispanics regarding ATTR CA prevalence, we further hypothesize that we will observe a prevalence of ATTRwt CA of 2-8% of the Hispanic population. Thus, we have conservatively defined the predicted prevalence of ATTR CA as 10-15%.

Hypothesis 2. Relative proportion of ATTR CA comprised by ATTRwt and ATTRm: As noted above, based upon the background allele frequency, we anticipate that Black patients will be much more likely to manifest ATTRm (Val122Ile) vs. ATTRwt CA, whereas Hispanic patients will be more likely to manifest ATTRwt CA. We will be able to explore the Val122Ile genotype frequency in the Hispanic population, and with the addition of cardiac amyloid scintigraphy scanning, the relative contribution of ATTRm in this population, which we postulate to be lower than Blacks. We will utilize genetic ancestry analysis data to further characterize race and ethnicity, and, as an exploratory analysis, evaluate the interaction of genetic variants identified with Val122Ile and ATTR CA as defined by radiotracer uptake.

Hypothesis 3. Proportion of gender: Published reports of ATTR Val122Ile are 75% male and reports of ATTRwt are 95% male. We hypothesize that highly sensitive cardiac amyloid scintigraphy testing will reveal a gender distribution of ATTR that is closer to 50%, based upon allele distribution. We will explore comorbidities, TTR stability, and RBP4 differences among men and women with ATTR to determine interactions with phenotypic expression.

Hypothesis 4. Progression of disease: Markers of disease progression are lacking in ATTR CA. We hypothesize that attainment of a hierarchical composite endpoint at 1-year of death, heart failure hospitalization, and 30% decline in 6-minute hall walk will be higher in ATTRm vs. ATTRwt CA. In addition, we will explore the capacity of specific markers to assess disease progression including: (1) established circulating biomarkers such as troponin I/T, NT-proBNP, BNP and Galectin-3, (2) novel biomarkers such as RBP4 and TTR concentration, (3) ECG, and

echocardiographic measures including longitudinal strain and MCF, (4) functional capacity by 6-minute hall walk and SPPB, and (5) QOL. Our preliminary data and published work⁹ suggests reduced median survival for ATTRm Val122Ile CA (25 months) vs ATTRwt (43 months) in different race cohorts. We hypothesize that we will observe reduced survival and greater functional decline in ATTR Val122Ile vs ATTRwt within race cohorts.

Hypothesis 5. Performance of risk calculator: Our point-of-care risk calculation utilizing RBP4 and TTR concentration with echocardiographic and ECG determined parameters will be tested in this cohort. We will re-derive the prediction model based upon clinical variables noted above. We anticipate showing a similar degree of accuracy (ROC AUC > 0.95) for identification of cases with ATTR vs. controls

Specific Aim 2: To demonstrate that circulating RBP4 concentration is integral to TTR tetramer stability, which in turn determines the clinical characteristics of ATTR CA. We will measure TTR tetramer stability and RBP4 concentration in serum and urine collected in Aim 1. The overall hypotheses of this Aim are that measurements of TTR kinetic stability, RBP4 and TTR concentration will differentiate patients with ATTR CA vs. non-amyloid HF controls and associate with disease progression and outcomes. Specific hypotheses are as follows:

Hypothesis 1: TTR kinetic stability and RBP4 concentration: We hypothesize that at baseline, TTR kinetic stability will be lower in ATTR CA vs. non-amyloid HFpEF, and that stability will be inversely proportional to plasma RBP4 concentration. We further hypothesize that TTR kinetic stability will be lower for ATTRm vs. ATTRwt.

Hypothesis 2: TTR kinetic stability and disease progression: We hypothesize that TTR stability will associate with the specific outcomes of survival and disease progression detailed in Aim 1, sub-aim 4. We will explore further TTR stability among patients with indeterminate grade 1 cardiac amyloid scintigraphy scan results (early disease), and hypothesize that stability will be lower than non-amyloid HF controls.

Hypothesis 3: Urinary RBP4 concentrations: We hypothesize that RBP4 will be lower in plasma and higher in urine indexed for renal function by urinary creatinine, and vitamin A concentration, among patients with ATTR CA vs. non-amyloid controls. Reduced RBP4 binding, owing to TTR kinetic instability in blood, will result in increased clearance (and higher urine levels) of the protein. We will also explore RBP4 concentrations among patients with indeterminate grade 1 cardiac amyloid scintigraphy scan results, and hypothesize that serum RBP4 will be lower and urinary RBP4 higher than non-amyloid HF controls.

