CLINICAL STUDY PROTOCOL

Screening for Cardiac Amyloidosis with Nuclear imaging in Minority Populations study (SCAN-MP)

Protocol Version:

4.2

Protocol Date:

June 24, 2022

ClinicalTrials.gov:

NCT03812172

Sponsor:

Columbia University Medical Center
Clinical Cardiovascular Research Laboratory for the
Elderly (CCRLE)
[name]
[name]

Sponsor-Investigator:

[name]
Co-Principal Investigator
[contact]

[name]
Co-Principal Investigator
[contact]

Site Investigator:

[name]
Site Investigator
[contact]

Collaborating Investigators: [name]
Abbott Diagnostics

[name]
Abbott Diagnostics

STUDY SYNOPSIS

Protocol Title	Screening for Cardiac Amyloidosis with Nuclear imaging in Minority Populations study (SCAN-MP)
Protocol Number	4.2
Design	
This is a multicenter, diagnostic screening study to evaluate the prevalence of wild-type and Val122Ile ATTR cardiac amyloidosis (ATTR-CA) in a population of Black and Hispanic subjects with heart failure at participating sites. ATTR-CA is an age-related infiltrative cardiomyopathy that causes heart failure and death that is frequently unrecognized and underdiagnosed.
 
Consented eligible patients will be evaluated for the presence and clinical manifestations of ATTR Cardiac Amyloidosis.
 
Patients will undergo a Screening/Baseline visit, using nuclear medicine screening and TTR genetic test. Those who have myocardial retention of the imaging radiotracer with a Perigini score ≥ 2 (uptake equal to bone) and/or H/CL ratio > 1.3 will be diagnosed with ATTR amyloidosis and followed up in 6 months and again at 12 months.

Study Sites	This study is to be conducted at five study sites: Recruitment and Screening at Harlem Hospital. All study procedures at NYP Allen Hospital, NYP Milstein Hospital, Boston University Medical Center and Yale New Haven Hospital.
Time on Study	The duration of patient participation in this study is approximately 12 months.
Primary Objective	To improve identification of minority patients with ATTR-CA and enhance the understanding of genotype-phenotype associations in Blacks/Hispanics with ATTR-CA due to the Val122Ile mutation or ATTR wild-type.
Sample Size	Up to 800 patients will be screened in this study.

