2.1.7 Statistical Considerations and Sample Size

Power and Sample Size: The total enrollment proposed for this study is of 800 subjects: 600 Blacks and 200 Hispanics. Amongst them, we expect approximately 80-160 ATTR CA subjects and 640-720 non-amyloid controls. The sample size planned for each race/ethnicity group achieves 80% power to

detect, as in Aim 1: (1) a prevalence of ATTR-CA of 10-15%, (2) a two-fold difference in the prevalence of ATTRm between Blacks and Hispanics (i.e., 0.08 vs 0.04, respectively), as well as, a similar difference in the prevalence of ATTRwt between Blacks and Hispanics, (3) a difference as small as 0.03 (if one truly exists) in the prevalence of ATTRwt with respect to gender (male) distribution between the two race/ethnic groups, and (4) in the ATTR CA group alone, we plan to measure the hierarchical composite endpoint of death, heart failure hospitalization, and 30% decline in 6-minute hall walk after 1 year. A two-sided logrank test with an overall sample size of 80 subjects (40 in the ATTRwt and 40 in the ATTRm) achieves 82% power at a 0.05 significance level to detect a hazard ratio (HR) of 0.44 when the proportion of patients that did not progress in the mutant group is 0.60. This corresponds to a minimum difference of 15% in the probability of not having progressed past 12 months between the two groups.

Aim 2 focuses on comparing differences in TTR kinetic stability and RBP4 concentration between ATTR CA (N=80-120) and the non-amyloid group (N=680-720). These sample sizes generate >95% power to detect: Hypothesis 1) a minimum difference in RBP4 of 5, assuming SDs of 9 and 20 for ATTR CA and non-amyloid, respectively; Hypothesis 2) a mean change difference in TTR stability as small as 0.01, SD of 0.002.

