3.4 Stopping Study Procedure Due to Adverse Event

In the ordinary ongoing off-label use of this procedure there have been no reports of serious adverse reactions. Nevertheless, the injection and scan procedure will be stopped and the results will be marked as incomplete if there are any adverse reactions during its administration as part of this study. The adverse reactions that will lead the investigators to stop the cardiac amyloid scintigraphy scanning portion of the study procedures include but are not limited to the events listed in the package insert: hypotension, fever, chills, nausea, vomiting and dizziness, as well as hypersensitivity reactions such as itching and various skin rashes.

The scan will also be stopped in cases of severe cardiac symptomology such as: chest pain, shortness of breath, palpitations, tachycardia. In such cases, other study procedures may be continued.

In addition, subjects will be asked to contact the investigators if any additional adverse or allergic reactions are noted within the first 24 hours following the injection. If any such events are reported, the principal investigator will determine if they are potentially related to the administration of the imaging agent. Appropriate clinical care will be advised for any events determined by the investigator to be related to the scanning injection, and information about the reactions will be reported as described below.

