Time between injection and acquisition: (ideally 3 hrs)
____ : ____ (hh:mm)Image duration: _____ counts
(750,000 minimum counts)**Adverse Reactions (AR)**Any AR to radiotracer injection? Yes No

If 'Yes', please check all that apply:

 Flushing Itching Hypotension Skin rash Fever Chest pain Chills Palpitations Nausea Tachycardia Vomiting Shortness of breath Dizziness Other (specify): _____**Difficulties with Scan**

Please note any difficulties in obtaining the scan. For example, difficulty positioning the participant, participant motion, etc. and any action taken to correct it.

Form Completed by: _____

CARDIAC AMYLOID SCINTIGRAPHY Findings Sheet**Nuclear Findings****Planar myocardial radiotracer uptake pattern:**

 Absent	 Diffuse
 Focal	 Focal on diffuse

Semi-quantitative visual grading of radiotracer uptake – based on “Planar” images:

- Grade 0: no uptake and normal bone uptake
- Grade 1: uptake less than rib uptake
- Grade 2: uptake equal to rib uptake
- Grade 3: uptake greater than rib uptake with mild/absent rib uptake

Was SPECT imaging performed? Yes No

If 'Yes':

Semi-quantitative visual grading of radiotracer uptake – based on “Planar” and “SPECT” images:

- Grade 0: no uptake and normal bone uptake
- Grade 1: uptake less than rib uptake
- Grade 2: uptake equal to rib uptake
- Grade 3: uptake greater than rib uptake with mild/absent rib uptake

Quantitative interpretation of radiotracer uptake:

H/CL ratio: ____ . ____

If SPECT or SPECT/CT done, blood pool activity:

- Absent
- Minimal
- Significant

Technical Findings**Study difficulties:**

- None
- Participant motion
- High background
- Inadequate count density
- Dose infiltration
- Delay in imaging
- Poor labeling
- Other, specify: _____

Artifact Findings**Incidental Findings***(Bone findings, hot spots, pleural or pericardial effusion, etc.)***Comments****Conclusion****Overall interpretation:**

- Not suggestive of ATTR
- Strongly suggestive of ATTR
- Equivocal for ATTR / Possible early ATTR

Study quality:

- Uninterpretable
- Poor
- Fair
- Good
- Excellent

ON-SITE FOLLOW-UP

1. Was the study visit conducted? Yes No

a. If no, did the patient drop out of the study? Yes No

If yes, date of drop out: ____ / ____ / _____

If yes, provide reason subject dropped out, and **go to #2**:

b. If no, did the subject die? Yes No

If yes, date of death: ____ / ____ / _____

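### Aim 1 prevalence is cases over total enrolment, but a case needs a positive scan, so enrolled participants without a usable scan count as non-cases and missing scans can only lower the estimate.

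*Combined protocol and SAP*

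**What the plan says.** Section 2.1.6 (Aim 1, Hypothesis 1) defines prevalence as the "number of cases with both ATTRwt and ATTRm CA as a percentage of total enrollment". Section 2.1.7 sets the planned denominator: "The total enrollment proposed for this study is of 800 subjects: 600 Blacks and 200 Hispanics". It then forecasts the split: "we expect approximately 80-160 ATTR CA subjects and 640-720 non-amyloid controls".

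Section 2.1.5.2 makes case status depend on the scan: a visual score of at least 2 and/or an H/CL ratio of at least 1.3, with myocardial retention confirmed by SPECT in every case. It gives no route to case status without a scan.

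The protocol foresees scans that yield no result. Section 3.4 says that the procedure will be stopped and that "the results will be marked as incomplete if there are any adverse reactions during its administration". The Findings Sheet in Appendix 4 has a study-quality box labelled "Uninterpretable" and a No box for whether SPECT was performed. On the baseline checklist the scan is the last item.

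Section 2.1.8 plans sample proportions with exact 95% confidence intervals. It names no evaluable set, no rule for missing scans and no sensitivity analysis. The dropout paragraph in section 2.2 deals with loss before the blood sample. It accepts that a participant may decline clinically recommended testing, but does not say how that person is counted.

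**The concern.** Numerator and denominator rest on different sets of people. Only participants with a usable scan can be cases, while everyone enrolled is in the denominator. No sentence calls an unscanned participant amyloid-negative, but the definition has that effect. Prevalence is the headline estimate of Aim 1, and a fraction built this way mixes disease frequency with scan completion. If completion also differed between groups, it would enter the comparison in Hypothesis 2.

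**Working it through.** **The plan's own figures.** Expected cases = prevalence × 800.
- 0.10 × 800 = 80 cases and 720 controls, as section 2.1.7 states.
- 0.15 × 800 = 120 cases and 680 controls, as the Aim 2 paragraph of that section states.
- The Aim 1 upper figure of 160 cases (640 controls) needs 20%, not 15%. That mismatch does not affect this point.

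In each pairing, cases and controls add up to 800 (80 + 720, 120 + 680, 160 + 640). The planning leaves no place for a participant whose status is unknown.

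**Direction.** Let m be the share of enrolled participants without a usable scan, p_s the prevalence in those scanned and p_u the prevalence in those not scanned.
- True prevalence = p_s(1 − m) + p_u·m
- Reported on total enrolment = p_s(1 − m)
- Bias = −p_u·m

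This is never positive, and is zero only if m = 0 or no unscanned participant has the disease. It holds whether or not missingness is related to disease.

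**Size.** Assume p_s = p_u = p. Then reported = p(1 − m), and the relative bias is m. The documents give no m, so this range is an assumption:

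| m (assumed) | true 10% | true 12.5% | true 15% |
|---|---|---|---|
| 0% | 10.0% | 12.5% | 15.0% |
| 5% | 9.5% | 11.9% | 14.25% |
| 10% | 9.0% | 11.25% | 13.5% |
| 15% | 8.5% | 10.6% | 12.75% |
| 20% | 8.0% | 10.0% | 12.0% |

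**Against sampling error.** With every scan done, the exact 95% interval is 8.0–12.3% for 80/800 and 12.6–17.7% for 120/800, half-widths of about 2.1 and 2.5 points. At m = 10% the bias is 1.0 and 1.5 points, roughly half of that. The interval on total enrolment first excludes the true value at about m = 21% (true 10%) or m = 17% (true 15%).

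**With the denominator changed** (true 10%, m = 10%, so 720 scanned and 72 cases):
- as written: 72/800 = 9.0% (95% CI 7.1–11.2)
- usable scans only: 72/720 = 10.0% (7.9–12.4)
- bounds: 72/800 = 9.0% if all 80 unscanned are negative; (72 + 80)/800 = 19.0% if all are positive

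The written rule thus reports the lower bound as the estimate.

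**Limit of the alternative.** On usable scans the estimate is p_s, and its bias is p_s − [p_s(1 − m) + p_u·m] = m(p_s − p_u). That is zero only if missingness is unrelated to amyloid status. It is smaller in size than p_u·m whenever p_u exceeds half of p_s.

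**The case against.** The strongest reply is that the sentence in section 2.1.6 mainly says that wild-type and mutant cases are pooled, that the forecast in section 2.1.7 is planning arithmetic, and that the real defect is an undefined evaluable set. It is true that nothing in words calls unscanned participants negative. But the denominator is stated, and no other section replaces it.

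Four further objections stand and limit the point.

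- **When enrolment happens.** Section 2.1.5 allows up to 4 weeks between screening and the study visit, and a reader might count everyone lost in that gap. Section 2.2 places the blood sample immediately after enrolment, and blood is drawn at the baseline visit, which would leave those people out. Yet the date of enrolment is a field on the demographics form, which the screening checklist lists. The documents do not settle this. Stopped and uninterpretable scans count on either reading.
- **Harlem.** The synopsis limits one site to "Recruitment and Screening at Harlem Hospital", and a reader might infer that its recruits go unscanned. The same entry places all study procedures at the other named hospitals. Nothing shows lower completion.
- **Group comparison.** An equal 8% prevalence with m = 5% in Blacks and 15% in Hispanics would give 7.6% against 6.8%. No section shows such a difference, and with equal m the ratio between groups is unchanged.
- **Frequency.** Section 3.4 reports no serious adverse reactions in ordinary use, the quality box carries no expected rate, and the exclusions for non-adherence and weight should limit non-completion. The share may be small.

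**Conclusion.** The point holds: this is a stated rule that gives a wrong result, not just missing detail. The direction with respect to missing scans is certain; the size is not. Assuming equal prevalence in scanned and unscanned participants, a 5–15% unscanned share understates prevalence by 5–15% in relative terms, and full scan completion removes the bias.

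A reader might infer that the estimate will fall below the hypothesised 10–15%. In expectation that follows only if the truth lies at or near the lower edge: a true 12.5% stays inside the range throughout the assumed 5–15%. Nor does the point establish that total error is downward, since false-positive scans would push the other way.

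**What to change.** In sections 2.1.6 and 2.1.8:

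1. Define the denominator of the primary prevalence estimate as enrolled participants with a completed, interpretable scan, and state when a participant counts as enrolled.
2. Report the number excluded and the reasons, by site and by race/ethnicity.
3. Give bounds with all unscanned participants counted as negative and then as positive. These must accompany the new denominator, because it is unbiased only if missingness is unrelated to amyloid status. Imputation from baseline data is optional.

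The cost is a few sentences, a slightly smaller n and a wider interval: at a true 10% with m = 10%, 7.9–12.4% on 720 against 8.0–12.3% had all 800 been scanned. No extra data collection is needed.

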2.1.1 Research Goal

The goal of our research is to change the approach to transthyretin cardiac amyloidosis, which is a devastating disease, by screening and early diagnosis, and by studying prospectively a cohort of older Blacks/Hispanics with heart failure in order to address the following aims and hypotheses:

Specific Aim 1: To determine the prevalence of ATTR CA in Caribbean Hispanics and Blacks with HF. The hypotheses to be tested include:

- (1) the prevalence of ATTR CA will be 10-15%
- (2) ATTRwt CA will be higher among Caribbean Hispanics compared to US Blacks, whereas the prevalence of ATTRm CA will be lower
- (3) the gender distribution of ATTR CA identified by this active ascertainment approach will be similar
- (4) disease progression will demonstrate that ATTRm is associated with a more rapid decline vs. ATTRwt
- (5) the accuracy of our clinic-based risk calculator will be confirmed in this large prospectively recruited cohort

Specific Aim 2: To demonstrate that circulating RBP4 concentration is integral to TTR tetramer stability which in turn determines the clinical characteristics of ATTR CA. We will measure TTR tetramer stability and RBP4 concentration in serum and urine collected in Aim 1. The hypotheses to be tested include:

- (1) TTR tetramer stability will be lower in ATTR CA and directly relate to RBP concentration
- (2) TTR tetramer stability will associate with clinical features and
- (3) Increased renal clearance of RBP4 in ATTR CA will be determined by measurement of RBP4 in plasma and urine.

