2.1.3 Patient Recruitment

The SCAN- MP study is designed to identify a sufficient number of cases to support the following analytical objectives:

1. Stratify prevalence of ATTR-CA in subjects with HF by relevant demographic characteristics (gender, race/ethnicity, genotype); and
2. Evaluate relationships among ATTR-CA and baseline risk factors (presence of Val122Ile mutation and others) with disease outcomes.

To accomplish these objectives, a hybrid approach to cohort identification and selection is used that combines deliberate selection of subjects with heart failure who are at increased risk for ATTR-CA and selection of participants with relevant characteristics (age, gender, race/ethnicity, country of origin). Planned proportion of enrolled subjects by relevant characteristics is shown in the Table 3. Community involvement is essential for its success and recruitment will involve intensive community engagement through various means among the sites. In aggregate, we will recruit an equal number of men and women from the racial/ethnic groups. The expected marginal distributions of race/ethnicity are shown in Table 3. We will have overlapping ethnic groups among centers to minimize confounding of ethnicity by site. As recruitment of elderly members of minority groups is challenging, toward end of the recruitment period, participants will be asked to refer elderly persons to the study.

Table 3. Planned Enrollment by Age, Race, and Gender

Age (yr)	Black		Hispanic or Latino ethnicity		Total	
	M	F	M	F	M	F
≤75	150	150	50	50	200	200
>75	150	150	50	50	200	200

At CUMC we have seen 24,682 unique patients with HF over the last five years of which 2,969 (12%) self-identified as Black and 4,387 of 14,466 (29.9%) patients who declared their ethnicity were Hispanic and whose average age was 63 years. Harlem Hospital provides health care services to the primary service area of Harlem, Washington Heights/Inwood and the South Bronx with the vast

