2.1.8 Data Analysis Plan

Descriptive statistics will be used to summarize subjects' demographics and study outcomes. Sample proportions with exact 95% confidence intervals will be used to estimate the overall prevalence of ATTRm CA in Blacks and Hispanics and by sex. All analyses will be performed in SAS v.9.4 (Cary,NC), at a significance level of 0.05.

AIM 1: Hypotheses 1-3: The differences in proportions for prevalence (#1), genetic mutation status (#2), and sex (#3) will be assessed using Chi-squared/Fisher Exact tests. The genetic ancestry analysis will use 500K SNP data to perform principal components analysis (PCA) and determine the percentage of African admixture in all participants. To identify the associations of rare genetic variants in the TTR gene in ATTR CA cases vs controls, we will utilize burden testing.⁹⁴ **Hypothesis 4:** The main analysis will use the Kaplan-Meier method to estimate the probabilities of the composite endpoint, with medians (95% CI) being reported for each group. Cox regression analysis will be performed to generate the hazard ratio (95% CI), and to allow adjustment for other covariates such as sex or race/ethnicity, or explore interaction with other variables including cardiac biomarkers, echo parameters, or QOL. Alternatively, we will apply and compare Finkelstein-Schoenfeld's unmatched approach⁹⁵ to the matched win ratio,⁹⁶ both methods being used for reporting composite endpoints, with more appropriate priority given to the more clinically important event, e.g. mortality. **Hypothesis 5:** We will test the clinic-based risk calculator that was previously developed and validated in a smaller matched cohort study.⁹⁷ The proposed 4-variable model included: RBP4, LVEF, inter-ventricular septal thickness, mean limb lead QRS voltage, and generated an ROC AUC >90%. This model will be tested in our larger cohort and assessed with respect to prediction capability (AUC ROC) and goodness-of fit (Hosmer-Lemeshow test). We also plan to fit additional multivariable logistic regressions using the variables collected employing variable selection/model-building strategies and comparing the

resulting model(s) to the one proposed above. The variables in the final clinical risk model will be based on weights from the multivariate model.

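### Aim 1 Hypothesis 3 predicts a similar sex distribution but is assessed only with a difference test, which can neither establish similarity nor compare the male share with the published 75% and 95%

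*Combined protocol and SAP*

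**What the plan says.** - Section 2.1.1 (Research Goal) lists, among the Aim 1 hypotheses to be tested, that "the gender distribution of ATTR CA identified by this active ascertainment approach will be similar".
- Section 2.1.6 (Aim 1, Hypothesis 3) gives the background: "Published reports of ATTR Val122Ile are 75% male and reports of ATTRwt are 95% male". It then predicts that the study "will reveal a gender distribution of ATTR that is closer to 50" percent. No tolerance around 50% is given.
- Section 2.1.8 (Data Analysis Plan) assesses differences in proportions for Hypotheses 1 to 3; the part on this hypothesis reads "and sex (#3) will be assessed using Chi-squared/Fisher Exact tests". All analyses are "at a significance level of 0.05".
- Section 2.1.8 also plans exact 95% confidence intervals to "estimate the overall prevalence of ATTRm CA in Blacks and Hispanics and by sex". It names no interval for ATTRwt by sex, for the male share of cases, or for the male-female difference.
- Section 2.1.7, item (3), claims 80% power for a 0.03 difference in ATTRwt prevalence with respect to gender, but the contrast it names is between the two race/ethnic groups.
- Section 2.1.3 states that "we will recruit an equal number of men and women from the racial/ethnic groups"; Table 3 gives 400 men and 400 women.
- The Synopsis (Aims) lists gender differences among the items to be explored.

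**The concern.** The hypothesis can be read in two ways, and the planned test answers neither.

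If the claim is similarity between the sexes, a difference test can reject equality but cannot establish it. A p-value above 0.05 becomes more likely as cases become fewer, whatever the true split.

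If the claim is a male share nearer 50% than the published figures, the comparators are 75% and 95%, and the test involves neither. It can also point the wrong way: a significant male excess at a true 60% share would look like refutation, although 60% is nearer to 50% than either published figure is.

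At stake is one of the five stated Aim 1 hypotheses. As written, no outcome of its named test could support it.

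**Working it through.** **1. The plan's own figure.** Section 2.1.7 gives no base rate for the 0.03 difference, so I scanned it with a two-sided pooled-variance z test at 0.05. Power within 2 points of 80% needs a lower rate of about 0.55-0.7% (600 Black v 200 Hispanic, Hispanic higher), 0-0.1% (Black higher) or 0.75-0.95% (400 men v 400 women). At 2% v 5%, power is 59%, 43% and 64% respectively. The figure can be neither confirmed nor refuted. On any reading it is power to detect a difference.

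**2. The planned test, read as men v women.** Inputs: 400 per sex (Table 3); C = 80 to 160 cases in all, and 40 of one type (both in section 2.1.7); two-sided 0.05 (sidedness is not stated for this test). For a true male share s, the prevalences are C·s/400 in men and C·(1−s)/400 in women. The statistic is z = [(x_m − x_f)/400] / √[2·p̄(1−p̄)/400], with p̄ = (x_m + x_f)/800; this is the uncorrected Chi-squared test. The probability that |z| < 1.96 comes from enumerating the two binomials.

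Worked case: 48 men and 32 women among 80 cases (12% v 8%). Then p̄ = 0.10, the standard error is √(2·0.1·0.9/400) = 0.0212, z = 0.04/0.0212 = 1.89 and p = 0.059. An observed 60% male share is therefore non-significant. Its exact 95% CI is 48-71%.

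Probability of a non-significant result:

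| True male share | 40 cases of one type | 80 cases | 120 cases | 160 cases |
|---|---|---|---|---|
| 60% | 75% | 53% | 34% | 19% |
| 65% | 51% | 19% | 5% | 1% |
| 70% | 25% | 3% | 0.2% | <0.1% |
| 75% | 9% | 0.2% | <0.1% | <0.1% |

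The largest non-significant observed splits are 48:32 (60% male) with 80 cases, 69:51 (57.5%) with 120, 91:69 (57%) with 160, and 26:14 (65%) with 40 of one type. In the other direction, a true 60% share with 160 cases is significant 81% of the time.

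**3. The contrast named in section 2.1.7.** Suppose the male share is compared between Black and Hispanic cases, assumed to split 3:1 as in enrolment (60 v 20 up to 120 v 40). If 75% are male in both groups, the test is non-significant about 95% of the time; at 95% male in both, 96-97%. That contrast says nothing about how near the share is to 50%.

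**4. What an interval would show.** Exact (Clopper-Pearson) 95% limits for the male share:

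- 20/40: 33.8-66.2%
- 40/80: 38.6-61.4%
- 60/120: 40.7-59.3%
- 24/40: 43.3-75.1%, which does not exclude 75%
- 34/40: 70.2-94.3%, which excludes 95% although 85% are male

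An exact one-sided 0.025 test against 75%, at a true 60% share, has 43% power with 40 cases, 79% with 80 and 92% with 120.

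**5. What a similarity claim would need.** The documents give no margin; ±10 and ±15 points around 50% are my assumptions. At a true 50% share, the chance that the 95% CI lies inside the margin m is approximately 2Φ(m/√(0.25/n) − 1.96) − 1, or 0 if that is negative. For 80, 120 and 160 cases this gives 0%, 18% and 43% at ±10 points, and 53%, 82% and 93% at ±15 points. With the 90% CI usual for equivalence (1.645 in place of 1.96), the values are 11%, 42% and 62%, and 70%, 90% and 97%.

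**The case against.** A reader might infer that the plan would take non-significance as confirmation even when men clearly predominate. The documents do not support either half of that. No rule for interpreting a non-significant result is written, so treating it as support is only a possible use. In the pooled men-v-women test, a true 70% share is missed at most 3% of the time and 75% at most 0.2%. Sizeable predominance can escape only with few cases, as within one type, or if the contrast is between ethnic groups.

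Other points carry weight:

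- Exact intervals for ATTRm prevalence by sex are already planned. With 1:1 recruitment they hold much of what is needed for that type. The gap is ATTRwt, all cases together, and the male share or difference itself.
- The Synopsis treats gender differences as exploratory, where a difference test with estimates is ordinary. Section 2.1.1, however, lists the same item as a hypothesis to be tested.
- The published shares are imperfect comparators. The documents do not give the sex mix of the populations behind them, and enforcing 1:1 recruitment could itself pull the male share toward 50%.
- An interval rule is no cure-all. Excluding 95% can coexist with 85% male, and 40 cases are too few to exclude 75% reliably if the truth is 60%.

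These points limit how strongly the problem can be stated, and they shape the fix. They do not make the planned test suitable for the stated hypothesis.

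**Conclusion.** The point stands: a hypothesis of similarity, or of a share below published values, is paired only with a test of difference, without a margin or a comparison with 50%, 75% or 95%, and the power statement addresses another contrast. The effect is moderate in the pooled analysis, where non-significance is compatible with an observed male share up to about 57-60%. It is larger within one type, where it extends to about 65% with 40 cases. The figures assume exactly 400 per sex, the case counts in section 2.1.7, a two-sided 0.05 level and an uncorrected Chi-squared test. The mismatch between hypothesis and test does not depend on them.

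**What to change.** In section 2.1.8, make estimation the main analysis for Hypothesis 3:

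1. Report the male-female prevalence difference or ratio with a 95% CI, and the male share of cases with an exact 95% CI, overall and for ATTRm and ATTRwt. This extends the by-sex intervals already planned for ATTRm. The Chi-squared or Fisher test may stay as a secondary result.
2. State that p > 0.05 is not evidence of similarity.
3. Claim similarity only if the CI lies within a pre-specified, justified margin around 50% male (or around zero difference).
4. Otherwise claim only that the share is below the published value for that type, when the upper limit excludes it. Note that 1:1 recruitment limits this comparison, and that excluding 95% alone does not show a share near 50%.
5. Align item (3) of section 2.1.7 with this contrast and state its base rate. Reconcile the wording in sections 2.1.1 and 2.1.6 and the exploratory listing in the Synopsis.

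Cost: plan wording and slightly more analysis, with no new data. The downside is that a similarity claim may not be reachable with few cases: under a ±10-point margin, about 215 cases would be needed for 80% power even with a 90% CI, and about 96 under ±15 points.
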